8.2 Comparability of Subjects at Baseline

The statistical significance of any treatment group difference in the distribution of categorical variables such as gender will be tested using Cochran–Mantel–Haenszel (CMH) test for general association adjusted for site. Continuous variables, such as age, will be analyzed using a two-way analysis of variance (ANOVA) model with site and treatment as a fixed effect.

9. CONSENT/ASSENT CONSIDERATIONS AND PROCEDURES

It will be made clear to the subject that, for the purposes of the study, they are consenting only for topical application of medication or vehicle. Investigators may discuss the availability of the study and the possibility for entry with a potential subject without first obtaining consent/assent. However, informed consent/assent must be obtained and documented prior to initiation of any procedures that are performed solely for the purpose of determining eligibility for research, including withdrawal from current medication(s). When this is done in anticipation of, or in preparation for, the research, it is considered to be part of the research.

The study must be approved in writing by an appropriate IRB as defined by FDA regulations. A copy of the Letter of Approval from the IRB, which also contains specific identification of the documents approved, must be received by Perrigo Pharmaceuticals, prior to study commencement.

Periodic status reports must be submitted to the IRB at least annually as required by the site's IRB, as well as notification of completion of the study and a final report within three months of study completion or termination. A copy of all reports submitted to the IRB must be sent to Perrigo Pharmaceuticals.

The investigator(s) has both ethical and legal responsibility to ensure that each subject being considered for inclusion in this study is given a full explanation of the protocol. This shall be documented on a written informed consent/assent form, which shall be approved by the same Institutional Review Board (IRB) responsible for approval of this protocol. Each informed consent/assent form shall include the elements required by FDA regulations in 21 CFR Part 50. The investigator agrees to obtain approval from Perrigo Pharmaceuticals of any written informed consent/assent form used in the study, preferably prior to submission to the IRB.

Once the appropriate essential information has been provided to the subject and fully explained by the investigators (or a qualified designee) and it is felt that the subject understands the implications of participating, the IRB-approved written informed consent/assent form shall be signed by the subject (or their parent/legally authorized representative) and the person obtaining consent/assent (investigator or designee). The subject shall be given a copy of the signed informed consent/assent form and the investigator shall keep the original on file.

Protocol No: PRG-NY-12-005

If the subject fails to meet the inclusion/exclusion criteria at the conclusion of the screening phase, the subject will be withdrawn from screening. In the event that the subject is re-screened for study participation, a new informed consent/assent form must be signed.

9.1 Subject Confidentiality

All participants are concerned for the individual subject's privacy and, therefore, all subject data will be identified only by a subject identification number and subject initials. However, in compliance with federal guidelines regarding the monitoring of clinical studies and in fulfillment of his/her obligations to Perrigo Pharmaceuticals, it is required that the investigator permit the study monitor, any Sponsor authorized representative, and/or FDA representative to review that portion of the subject's medical record that is directly related to the study. This shall include all study relevant documentation including subject medical histories to verify eligibility, laboratory test result reports to verify transcription accuracy, admission/discharge summaries for hospital stays occurring while the subject is enrolled in the study and autopsy reports for deaths occurring during the study.

As part of the required content of informed consent, the subject must be informed that his/her medical chart may be reviewed by Perrigo Pharmaceuticals or their authorized representative, or a representative of the FDA. Should access to the medical record require a separate waiver or authorization, it is the investigator's responsibility to obtain such permission from the subject in writing before the subject is entered into the study.

To preserve the subject's confidentiality, the data collected will be available only to the investigators of the study, their support staff, Perrigo Pharmaceuticals or their authorized representative and possibly the FDA.

All reports and communications relating to the subject in the study will identify each subject only by the subject's initials and by the subject number. The investigator agrees to furnish Perrigo Pharmaceuticals with complete subject identification, if necessary on a confidential follow-up form, which will be used for the purpose of a long-term follow-up, if needed. This will be treated with strict adherence to professional standards of confidentiality and will be filed at Perrigo Pharmaceuticals under adequate security and restricted accessibility.

10. CONDUCT OF STUDY

The investigational site is to maintain complete documentation of all events and the times at which they occur.

10.1 Completion of Study

The investigational site will complete the study and complete all documentation required, in satisfactory compliance with the protocol, within 3.5 months of enrollment of the last subject and extending beyond as needed to complete necessary data queries.

It is agreed that, for reasonable cause, either the investigator or Perrigo Pharmaceuticals may terminate this study before completion provided written notice is submitted at a reasonable time

in advance of intended termination. Any extension of this study must be mutually agreed upon in writing by both the investigator and Perrigo Pharmaceuticals.

10.2 Protocol Amendments

The Investigator will not make any changes to this protocol without prior written consent from Perrigo Pharmaceuticals and subsequent approval by the IRB. Any permanent change to the protocol, whether it is an overall change or a change for specific study center(s), must be handled as a protocol amendment. Any amendment to the protocol that appears indicated as the study progresses will be fully discussed between [REDACTED] and Perrigo Pharmaceuticals. If agreement is reached regarding the need for an amendment, the amendment will be written by Perrigo Pharmaceuticals. The written amendment must be submitted to the chairman of the IRB identified with this responsibility. Except for 'administrative amendments', investigators must await IRB approval of protocol amendments before implementing the change(s). Administrative amendments are defined to have no effect on the safety of the research subjects, scope of the investigation, or quality of the trial. However, a protocol change intended to eliminate an apparent immediate hazard to subjects should be implemented immediately, and the IRB notified within five days. Perrigo Pharmaceuticals will submit protocol amendments to the FDA or other regulatory agencies.

When, in the judgment of the reviewing IRB, the investigators and/or Perrigo Pharmaceuticals, the amendment to the protocol substantially alters the study design and/or increases the potential risk to the subject, the currently approved written informed consent form will require similar modification. In such cases, repeat informed consent will be obtained from subjects enrolled in the study before expecting continued participation.

11. RECORDS MANAGEMENT

11.1 Data Collection

All data collected in this study will be entered onto CRFs, verified by monitoring, submitted for double key entry into an appropriate database, and submitted for statistical evaluation as described below. Checks will be run on the data and queries issued as needed. Once all data is cleaned, full quality control verification will be done prior to breaking the blind. After all data are correctly entered, the database will be locked and submitted for appropriate Quality Assurance verifications before the treatment assignment code is broken. All data collected in the CRFs will be documented in subject data listings and summarized in tables, as appropriate.

During each subject's visit to the clinic, a designee participating in the study will record progress notes to document all significant observations. At a minimum, these notes will contain:

- a) Documentation of the informed consent process;
- b) The date of the visit and the corresponding Visit or Week in the study schedule;
- c) General subject status remarks, including any *significant* medical findings. The severity, frequency, and duration of any adverse events and the investigator's assessment of relationship to study medication must also be recorded.
- d) Any changes in concomitant medications or dosages;

- e) A general reference to the procedures completed; and
- f) The signature (or initials) and date of all clinicians who made an entry in the progress notes.

In addition, any contact with the subject via telephone or other means that provides significant clinical information will also be documented in the progress notes as described above.

Any changes to information in the study progress notes and other source documents, will be entered in **black ink, initialed and dated** by the authorized person making the correction/addition. Changes will be made by striking a single line through erroneous data, and clearly entering the correct data. (e.g., ~~wrong data~~ right data). Entries may not be erased or masked with white-out fluid. If the reason for the change is not apparent, a brief explanation for the change will be written adjacent to the change by the clinician.

For transmission to Perrigo Pharmaceuticals, information from the study progress notes and other source documents will be promptly entered into the database. The database also contains a complete audit trail to capture all regulatory components of data corrections (e.g. initial entry, new value, initials and date of the change).

11.2 Source Documents

Source documents are defined as the results of original observations and activities of a clinical investigation. Source documents will include, but are not limited to, progress notes and screening logs. All source documents pertaining to this study will be maintained by the investigators and made available for inspection by authorized persons. The original signed informed consent form for each participating subject shall be filed with records kept by the investigators and a copy given to the subject.

11.3 File Management at the Study Site

It is the responsibility of the investigator to ensure that the study center file is maintained in accordance with Section 8 of the International Conference on Harmonization (ICH) Guideline for Good Clinical Practices (GCP).

11.4 Records Retention at the Study Site

FDA regulations require all investigators participating in clinical drug studies to maintain detailed clinical data for one of the following periods:

- a) A period of at least two years following the date on which a New Drug Application is approved by the FDA;
- b) A period of two years after Perrigo Pharmaceuticals notifies the investigator that no further application is to be filed with the FDA.

The investigator must not dispose of any records relevant to this study without either (1) written permission from Perrigo Pharmaceuticals or (2) providing an opportunity for Perrigo Pharmaceuticals to collect such records. The investigator shall take responsibility for maintaining adequate and accurate electronic or hard copy source documents of all observations and data

generated during this study, including any data clarification forms (DCFs) received from [REDACTED]
[REDACTED] Such documentation is subject to inspection by Perrigo Pharmaceuticals and the FDA.

12. QUALITY CONTROL AND QUALITY ASSURANCE

12.1 Monitoring

Perrigo Pharmaceuticals has ethical, legal and scientific obligations to carefully follow this study in a detailed and orderly manner in accordance with established research principles and FDA regulations. All medical records (source documents) of the subjects participating in this study must be presented for review and verification of CRFs.

12.2 Auditing

Perrigo Pharmaceuticals (or representative) may conduct audits at the study center(s). Audits will include, but are not be limited to, drug supply, presence of required documents, the informed consent process, and comparison of case report forms with source documents. The investigator agrees to participate with audits conducted at a reasonable time in a reasonable manner.

Regulatory authorities worldwide may also audit the investigator during or after the study. The investigator should contact Perrigo Pharmaceuticals immediately if notified of such an audit, and must fully cooperate with the audits conducted at a reasonable time in a reasonable manner.

13. ETHICS AND RESPONSIBILITY

This study must be conducted in compliance with the protocol, the United States Food and Drug Administration (FDA) regulations, any other countries regulations, and ICH GCP Guidelines.

14. USE OF INFORMATION AND PUBLICATION

All information supplied by Perrigo Pharmaceuticals in connection with this study and not previously published, is considered confidential information. This information includes, but is not limited to, data, materials (i.e. the clinical protocol, case report forms), equipment, experience (whether of a scientific, technical, engineering, operational, or commercial nature), designs, specifications, know-how, product uses, processes, formulae, costs, financial data, marketing plans and direct selling systems, customer lists and technical and commercial information relating to customers or business projections used by Perrigo Pharmaceuticals in its business. Any data, inventions, or discoveries collected or developed, as a result of this study is considered confidential. This confidential information shall remain the sole property of Perrigo Pharmaceuticals, shall not be disclosed to any unauthorized person or used in any unauthorized manner without written consent of Perrigo Pharmaceuticals, and shall not be used except in the performance of the study. As such, confidential study-related information should not be included on the curriculum vitae of any participating investigator or study staff.

The information developed during the course of this clinical study is also considered confidential, and will be used by Perrigo Pharmaceuticals in connection with the development of the drug. The information may be disclosed as deemed necessary by Perrigo Pharmaceuticals to allow the use of the information derived from this clinical study, the investigator is obliged to provide Perrigo Pharmaceuticals with complete test results and all data developed in the study. The information [REDACTED]

Protocol No: PRG-NY-12-005

obtained during this study may be made available to other investigators who are conducting similar studies.

The investigator shall not make any publication related to this study without the express written permission of Perrigo Pharmaceuticals. [REDACTED]

[REDACTED]

[REDACTED]

[REDACTED]

Protocol No: PRG-NY-12-005

INVESTIGATOR AGREEMENT

PROTOCOL NUMBER: PRG-NY-12-005

15.3 Appendix C: [REDACTED]

[figure not shown]
Protocol No: PRG-NY-12-005

[figure not shown]
Protocol No: PRG-NY-12-005

[figure not shown]
Protocol No: PRG-NY-12-005

[figure not shown]
Protocol No: PRG-NY-12-005

[figure not shown]
Protocol No: PRG-NY-12-005

Protocol No: PRG-NY-12-005

Protocol No: PRG-NY-12-005

**List of Abbreviations**

AE	Adverse Event
ANOVA	Analysis of Variance
CI	Confidence Interval
CMH	Cochran-Mantel Haenszel
IGA	Investigator's Global Assessment
ITT	Intent to treat population
LOCF	Last Observation Carried Forward
MedDRA	Medical Dictionary for Regulatory Activities
mITT	Modified Intent To Treat population
PD	Protocol Deviation
PP	Per protocol population
PV	Protocol Violation
SAE	Serious Adverse Event
SAP	Statistical Analysis Plan
TEAE	Treatment-Emergent Adverse Event
TESAE	Treatment-Emergent Serious Adverse Event
WHO Drug	World Health Organization Drug Dictionary

## Statistical Analysis Plan

### 1 Purpose of Statistical Analysis Plan

The purpose of the statistical analysis plan is to describe in detail all the data, statistical methods, and summary tables required to implement the statistical analysis of Clinical Study Protocol PRG-NY-12-005

### 2 Study Objectives

To compare the efficacy and safety profiles of Perrigo Israel Pharmaceuticals, Ltd.; Clindamycin Phosphate and Benzoyl Peroxide Topical Gel 1.2%/2.5% and Acanya® Topical Gel (Clindamycin Phosphate and Benzoyl Peroxide Gel 1.2%/2.5%) and to show the superior efficacy of the two active formulations over that of the vehicle in the treatment of Acne Vulgaris.

### 3 Study Design

For the purpose of exploring the above objectives, the study will be conducted as a double-blind, randomized, parallel-group, vehicle-controlled, multicenter trial.

The actual number of subjects enrolled in the study will be based on blinded review of subject status (related to the per-protocol (PP) definition under [section 4](#)) to determine that the number of subjects expected to meet the PP criteria is sufficient [REDACTED]. If this number is expected to be met prior to enrolling [REDACTED] subjects, the enrollment will be closed.

[REDACTED]

Each subject will be randomly assigned to one of following treatment groups [REDACTED]:

- (1) Test: Clindamycin Phosphate and Benzoyl Peroxide Topical Gel 1.2%/2.5%, [REDACTED]
- (2) Reference: Acanya® Topical Gel (Clindamycin Phosphate and Benzoyl Peroxide Gel 1.2%/2.5%), Valeant Pharmaceuticals (Dow Pharmaceutical Sciences, Inc)
- (3) Vehicle of test product [REDACTED]

Subjects will be admitted into the study only after written informed consent has been obtained and all of the inclusion and none of the exclusion criteria have been met. Randomization will be performed according to a computer generated randomization scheme where the treatment group designation has been assigned to the subject number. The treatment designation will remain blinded until the final database is closed. An independent third party generator will generate and hold the randomization code throughout the study. Randomized subjects will apply [REDACTED] to the affected areas of the face avoiding contact with the eyes, mouth, lips, inside and on angles of the nose, and mucous membranes once daily for 12 weeks.

Subjects will be scheduled for an office visit for Visit 1/Day 1 (Baseline), Visit 2/Week 4/Day 28 ( $\pm 4$  days) (Interim), Visit 3/Week 8/Day 56 ( $\pm 4$  days) (Interim), and Visit 4/Week 12/Day 84 ( $\pm 4$  days) (End of treatment, end of study). Safety will be assessed by monitoring adverse events at each visit and at the Week 2/Day 14 ( $\pm 4$  days) Telephone Contact.

#### 4 Populations To Be Analyzed

Three subject populations are defined as follows:

- (1) An intent-to-treat (ITT) subject is any individual who: (a) was randomized into the study, received and (b) applied at least one dose of study medication;
- (2) A modified intent-to-treat (mITT) subject is any individual who: (a) met inclusion/exclusion criteria, (b) was randomized into the study, (c) received and applied at least one dose of study medication, and (d) had at least one post-baseline efficacy assessment for the two lesion types;
- (3) A per-protocol (PP) subject, consistent with the protocol, is one that: (a) met inclusion/exclusion criteria, (b) was randomized into the study, received and used study medication, (c) [REDACTED] (d) returned for Visit 4/ Week 12 (End of Treatment/Early Termination Visit) within the specified window ( $+/- 4$  days) and had data on lesion count, OR was discontinued early due to treatment failure [REDACTED]  
[REDACTED] and (e) took no concomitant medications prohibited by the protocol or had any other significant protocol violations, and

[REDACTED]  
[REDACTED]  
[REDACTED]  
[REDACTED]

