4.2 Exclusion Criteria

Subjects may **not** be selected if any of the following criteria exist:

1. Subjects, who are pregnant, breast feeding, or planning a pregnancy within the study participation period.
2. Presence of [REDACTED] facial nodulocystic lesions (i.e. nodules and cysts).
3. [REDACTED]
4. [REDACTED].
5. [REDACTED]
6. [REDACTED]
7. Presence of any other facial skin condition that might interfere with acne vulgaris diagnosis and/or assessment [REDACTED]
[REDACTED]
[REDACTED]
8. Excessive facial hair [REDACTED] that would interfere with diagnosis or assessment of acne vulgaris.
9. History of unresponsiveness to topical Clindamycin Phosphate and/or benzoyl peroxide therapy.
10. Use of systemic Clindamycin products [REDACTED] prior to baseline or throughout the study.
11. History of hypersensitivity or allergy to Clindamycin Phosphate, benzoyl peroxide and/or any ingredient in the study medication.
12. Use [REDACTED] prior to baseline or during the study of oral retinoids (e.g. Accutane®) or therapeutic vitamin A supplements of greater than 10,000 units/day [REDACTED]
[REDACTED]
13. Use [REDACTED] prior to baseline or during the study of therapeutic vitamin D supplement [REDACTED]
14. Use of medications known to exacerbate acne [REDACTED]
[REDACTED]
15. [REDACTED]
[REDACTED]
[REDACTED]
16. Use of medicated make-up throughout the study and significant change in the use of consumer products [REDACTED] and throughout the study (other than study supplied cleanser and lotion).
17. Use [REDACTED] prior to baseline or during the study of 1) systemic steroids*, 2) systemic (e.g., oral or injectable) antibiotics, 3) systemic treatment for acne vulgaris (other than oral retinoids which require a 6-month washout), or 4) systemic anti-inflammatory or immunosuppressive agents [REDACTED].
[REDACTED]

18. [REDACTED]

19. [REDACTED]

20. [REDACTED]

21. Subject consumes excessive alcohol, abuses drugs, or has a condition that could compromise the subject's ability to comply with study requirements.

22. [REDACTED]

23. [REDACTED]

24. [REDACTED]

25. Previous enrollment in this current study.

26. [REDACTED]

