5.17 Discontinuation/Withdrawal of Study Subjects

Subjects may be removed from the study for any of the following reasons:

- The subject withdraws his or her consent for any reason.
- The subject's condition has worsened to the degree that the investigator feels it is unsafe for the subject to continue in the study.

- The subject's medication code is unblinded.
- Subject did not meet or no longer meets the entry criteria.
- An adverse event occurs for which the subject desires to discontinue treatment or the investigator determines that it is in the subject's best interest to be discontinued.
- The subject is lost to follow-up. The investigator will document efforts to attempt to reach the subject twice by telephone and will send a certified follow-up letter before considering that subject lost to follow-up. All attempts must be thoroughly recorded.
- The subject becomes pregnant during the course of the trial.
- [REDACTED]
- [REDACTED]

The reasons for a subject being discontinued will be documented in the case report form and the enrollment log.

If a subject is discontinued from the study for any reason, the Visit 4/ End of Study Visit/Early Termination Visit procedures should be completed and any outstanding data and study medication should be collected. Data, in addition to the reason for discontinuation and the date of removal, will be recorded on the End of Study Case Report Form.

[REDACTED]

[REDACTED]

[REDACTED]

[REDACTED]

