8.1 Statistical Analysis Plan

8.1.1 Analysing Populations

The following populations are defined for the purpose of analyses:

- Intent-to-Treat (ITT) (safety population): Any subject that was randomized received and used study medication.
- Modified Intent-to-Treat (mITT): Any subject, who met the inclusion/exclusion criteria, was randomized, received and used the study medication, and returned for at least one post-baseline efficacy assessment.
- Per Protocol (PP): Any subject:
 - Who met inclusion/exclusion criteria,
 - Who was randomized and received and used study medication.
 - Who met the protocol criteria for compliance [REDACTED] and [REDACTED]
 - Who completed Visit 4/Week 12 (End of Treatment/Early Termination Visit) within window [REDACTED]
 - Without significant protocol violations that could have interfered with the administration of the treatment or the precise evaluation of treatment efficacy.

A horizontal strip of black redaction bars, consisting of several thick black bars of varying lengths placed side-by-side, obscuring text or information.

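### Could the mITT condition on eligibility criteria remove subjects for prohibited use after randomisation?

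*SAP*

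**What the plan says.** The mITT definition in SAP section 4 opens with "a) met inclusion/exclusion criteria, (b) was randomized into the study, (c) received and applied at least one dose of study medication". Protocol 8.1.1 defines the same set as "Any subject, who met the inclusion/exclusion criteria, was randomized, received and used the study medication, and returned for at least one post-baseline efficacy assessment". Neither gives a time point, and neither sentence has a blackout inside it.

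The PP definition in SAP section 4 repeats the eligibility condition and adds a further one that mITT lacks: "e) took no concomitant medications prohibited by the protocol or had any other significant protocol violations".

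Protocol 4.2 introduces the exclusion list as conditions under which a subject may not "be selected if any of the following criteria exist". Some entries run past baseline. Criterion 16 begins "Use of medicated make-up throughout the study and significant change in the use of consumer products", and criterion 17 covers use "prior to baseline or during the study of 1) systemic steroids*, 2) systemic (e.g., oral or injectable) antibiotics, 3) systemic treatment for acne vulgaris".

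Two other places speak of meeting the criteria. Protocol 9 says "If the subject fails to meet the inclusion/exclusion criteria at the conclusion of the screening phase, the subject will be withdrawn from screening". Protocol 5.17 lists, among the reasons for removing a subject from the study, "Subject did not meet or no longer meets the entry criteria".

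Protocol 8.1.2 runs the efficacy analysis in both PP and mITT.

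**The concern.** If an exclusion criterion covers use during the study, a subject who was eligible on Day 1 can come to breach it in Week 6. Read literally, such a subject has not met the criteria and leaves mITT. Taking a systemic antibiotic or another acne treatment may itself depend on how well the assigned gel is working, so the mITT set would then be selected on behaviour that follows randomisation. Coding the flag blind would not cure that. The mITT set would also drift towards PP, which would weaken the point of analysing both. The phrase in Protocol 5.17 about a subject who ceases to meet the entry criteria shows that the protocol can use the criteria in a continuing sense.

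**Working it through.** **1. How many criteria carry on-study wording (Protocol 4.2).**
- Numbered exclusion criteria: 26.
- Fully blacked out: 3, 4, 5, 6, 15, 18, 19, 20, 22, 23, 24, 26 = 12.
- Legible at least in part: 1, 2, 7 to 14, 16, 17, 21, 25 = 26 − 12 = 14.
- Of those 14, naming use during or throughout the study: 10, 12, 13, 16, 17 = 5.

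So the count is 5 of 14. All five are themselves partly blacked out.

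**2. Which reading the text supports.**

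For eligibility at entry:
- The stem of Protocol 4.2 is about selection.
- SAP section 3 admits subjects only once the inclusion criteria are satisfied and no exclusion applies.
- Protocol 9 ties failure of the criteria to the end of screening.
- Both mITT definitions run in time order: criteria, randomisation, dosing, post-baseline assessment. The criteria come before randomisation.
- PP contains both the eligibility condition and item (e). If the first already covered on-study prohibited medication, much of the second would be redundant.
- A blanket whole-study reading fails on its own terms. Protocol 5.7 requires an IGA of at least 3 for enrolment. Success is a fall of at least 2 grades, so 3 becomes at most 1 and 4 at most 2, both below 3. If entry requirements had to hold throughout, every IGA success would leave the set. A literal reader would have to extend some criteria past entry and not others, with no rule for doing so.

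For a continuing test:
- Protocol 5.17. But that sentence separates a subject who failed at entry from one who lapses later, and it governs removal from the study, not analysis sets.

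**3. Can on-study wording be judged at entry?** These documents already treat future conduct as an entry test. Inclusion criterion 5 asks whether the subject will refrain from other topical acne products over the 12 weeks and respect the therapy prohibitions. Exclusion criterion 1 covers an intended pregnancy. Criteria 10, 12, 13, 16 and 17 can be read the same way, as expected use. That includes the make-up clause of criterion 16, which has only on-study wording.

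**4. Size.** On the entry reading nobody moves, so the change is zero.

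For the literal reading the documents give no inputs, so everything here is assumed: mean reduction 50% on active with nobody removed, 30% on vehicle, a fraction *p* of vehicle subjects removed, and a mean reduction *u* among those removed. The vehicle mean after removal is (30 − *p*·*u*)/(1 − *p*).

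| *p* | *u* | Vehicle mean | Active − vehicle |
|---|---|---|---|
| none removed | – | 30 | 20 |
| 0.02 | 0 | 30/0.98 = 30.6 | 19.4 |
| 0.02 | 60 | 28.8/0.98 = 29.4 | 20.6 |
| 0.10 | 0 | 30/0.90 = 33.3 | 16.7 |
| 0.10 | 60 | 24/0.90 = 26.7 | 23.3 |

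The difference shrinks if the removed subjects did badly and grows if the other treatment worked for them. The table shows only that the sign is undetermined.

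**The case for a change.** The best case for a change is that an analysis flag should not rest on inference. No legible sentence says that prohibited use leaves a subject in mITT, and PP item (a) uses the same words as mITT item (a), so the separation is implied only. There is also a plausible route to the problem. Protocol 5.12.6 lets a worsening subject be discontinued as a treatment failure and be advised standard treatment, and no legible text says how later treatment bears on the mITT condition. A clarifying clause before database lock would cost almost nothing.

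It stands that the time point is not written down. The rest carries less weight. The treatment-failure route concerns a subject who is being discontinued, whereas the five criteria speak of use during the study. The obvious insertion, that criteria are met as assessed at baseline, raises a question of its own: does a subject judged eligible on Day 1 but later found to have been ineligible stay in mITT? The present wording, with its plain past tense, arguably handles that case better. Finally, text after the population definitions in both documents is blacked out and may already settle the point.

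**Conclusion.** No change to the plan follows. The omission is real but small: one condition lacks an explicit time point, and 5 of 14 at least partly legible exclusion criteria contain wording that could prompt the question. The legible context resolves it as eligibility at entry, including ineligibility that comes to light later, with prohibited use after randomisation considered only for PP under item (e). A competent analyst would build the mITT flag that way.

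On that reading the effect on every result is nil. Under the literal reading the effect has no derivable size or direction, and the legible text does not show which primary comparison relies on mITT. The conclusion rests on the visible text and assumes that the blacked-out parts do not adopt the continuing sense. A sponsor who wishes to record the entry reading may do so, but nothing here requires it.
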